8.3.6 Pharmacodynamic Analysis

Descriptive statistics will be provided by change from baseline and percentage change from baseline as appropriate for:

- Fecal calprotection
- Eosinophil count, serum eotaxin-1,hs-CRP and ECP
- Change in eotaxin-1 concentration and eosinophil count in biopsy tissue from Screening to Day 56.

8.3.7 Safety Analysis

The evaluation of safety endpoints will be carried out on the Safety set. Safety will be assessed by evaluation of adverse events and changes from baseline in vital signs, physical examination, infusion reactionand clinical laboratory safety test results. Individual subject listing will be provided. The observation period for all the safety endpoints spans from start of study medication up to study day 90.

8.3.7.1 Adverse Events

Adverse events will be coded to system organ class and preferred term using the latest version of Medical Dictionary for Regulatory Activities (MedDRA) and are graded by the Investigator in terms of severity and relation to study treatment. All data will be listed by subject. Only treatment emergent AEs (TEAEs) will be presented in summary tables.

TEAEs are the adverse events that occur during the observation period, and the pre-treatment adverse events or pre-existing medical conditions that worsen in intensity after start of study medication and within the observation period.

TEAEs will be summarized by treatment arm in terms of crude incidence rates. For each event the crude incidence rate is defined as the number of subjects experiencing the event divided by the number of subjects initially exposed to study drug, regardless of duration of exposure to study drug. In addition, for each event the worst severity grade and the "worst" Investigator's judgment on study drug relationship is considered for each subject and frequency tables by worst severity grade and by worst study drug relation are provided. In this analysis, a subject having experienced more than once events classified under the same preferred term (body system) will be counted only once in the number of subjects with that preferred term (body system).

Summaries of TEAEs will be presented by body system and by preferred term within each body system (MedDRATM Terminology). The percentage of subjects who experienced AEs coded with the same term will be tabulated by treatment group in descending order according to the incidence of AEs in the active treatment groups.

All reported adverse events will be listed independently of their onset date. Serious Adverse Events, causes of death and AEs leading to premature discontinuation of study drug will be summarized similarly and listed. Reasons for premature discontinuation of study drug will be listed and summarized by frequency tables on all analysis sets.

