4.5 REMOVAL, REPLACEMENT, OR EARLY DISCONTINUATION OF SUBJECTS FROM THERAPY OR ASSESSMENT

Subjects are free to discontinue their participation in the study at any time and without prejudice to further treatment. The Investigator must withdraw any subject from the study if that subject requests to be withdrawn, or if it is determined that continuing in the study would result in a significant safety risk to the subject. Withdrawn subjects will not be replaced.

The subject's participation in this study may be discontinued due to the following reasons:

- Subject withdraws consent.
- Intolerable adverse event (any subject experiencing a grade 3 or 4 infusion reaction will be withdrawn from the study).
- Subject's need for medication prohibited by the protocol.

- The Investigator decides that continuing in the study would not be in the subject's best interest.
- The subject is noncompliant with the protocol.
- The subject becomes pregnant.
- Upon the decision of relevant Regulatory Authorities and/or the Institutional Review Board/Independent Ethics Committee (IRB/IEC).

Subjects who progress and/or relapse will be withdrawn from the study at the Investigator's discretion and will be able to receive local standard-of-care.

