4.5.1 Handling of Early Discontinuation

If a subject is withdrawn from the study, either at his or her request or at the Investigator's discretion, or fails to return, every effort should be made to determine the reason. This information will be recorded on the subject's case report form (CRF). All subjects who withdraw from the study prematurely, regardless of cause, should undergo Early Discontinuation Study Visit (see Section 5.4). It is important to obtain follow-up data for any subject withdrawn due to an AE or abnormal laboratory test finding. In any case, every effort must be made to undertake safety follow-up procedures.

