#### 8 Data Derivation and Transformation

Data not originally part of CRF will be derived as follows:

- Subjects age [years] = [Date of Informed Consent Date of Birth] / 365.25
- Study Duration [days]= Date of Last Visit Date of First Visit + 1.
- BMI = Weight (kg) / Height (m) $^2$
- Coding of Adverse Events will be done using MedDRA version 21.0.
- Coding of Concomitant Medication will be done using WHODrug Dictionary 2018.
- Mayo score will be calculated as sum of 4 sub-scores: Stool Frequency Sub-score, Rectal Bleeding Sub-score, Endoscopic Finding Sub-score and Physician's Global Assessment Sub-score, each of which ranges from 0 (normal) to 3 (severe disease). The sub-scores are summed to give a total score that ranges from 0–12.
- Partial Mayo Score will be calculated as sum of the 3 following sub-scores:
   Stool Frequency Sub-score, Rectal Bleeding Sub-score and Physician's Global

Assessment Sub-score. The sub-scores are summed to give a total score that ranges from 0–9.

- UCEIS score will be calculated as sum of 3 sub-scores: Vascular pattern (which range from 0 to 2), Bleeding (range from 0 to 3) and Erosions and Ulcers (range from 0 to 3). The sub-scores are summed to give a total score that ranges from 0–8.
- Baseline values will be taken as the last available pre-treatment measures.

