#### **Study termination**:

• Frequency of subjects who completed the trial

- For those subjects who did not complete the trial, frequency of the primary reason for premature discontinuation
- Listing of all dropouts along with reason for termination and supportive information if available, treatment and time of termination

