#### **Adverse Events (AEs):**

All treatment-emergent adverse events (including serious) will be tabulated using incidence tables with number and percentage of subjects by:

- System Organ Class (SOC) and Preferred Term
- Maximal Severity, System Organ Class (SOC) and Preferred Term

 Maximal Relation to study drug, System Organ Class (SOC) and Preferred Term

In the above frequency tables, the number and percentage of subjects who experienced AEs coded with the same preferred term will be tabulated by treatment group in descending order according to the incidence of AEs in the treatment group.

- By subject listing of all Adverse Events including subject ID, center, adverse
  event description, start date and time, intensity, whether treatment-emergent,
  relationship to study drug, action taken with study drug, corrective
  measurement, whether serious, seriousness specification, outcome, date and
  time of outcome
- Serious Adverse Events (SAEs):
   Same as the previous bullet (Adverse Events), limited to Serious Adverse Events only.

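### Crude adverse-event percentages ignore unequal follow-up if relapse withdrawals differ by arm, and no planned output summarises time at risk by arm

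*Protocol*

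**What the plan says.** **Rate.** Protocol 8.3.7.1 defines crude incidence thus: "number of subjects experiencing the event divided by the number of subjects initially exposed to study drug, regardless of duration of exposure to study drug". SAP 9.3 says that treatment-emergent events "will be tabulated using incidence tables with number and percentage of subjects by" system organ class and preferred term, and also by maximal severity and maximal relation to study drug. Neither document plans a rate per unit of time or a cumulative incidence.

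**Window.** Protocol 8.3.7: "The observation period for all the safety endpoints spans from start of study medication up to study day 90".

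**Leaving the study.** Protocol 4.5: "Subjects who progress and/or relapse will be withdrawn from the study at the Investigator's discretion". Protocol 4.5.1 adds: "All subjects who withdraw from the study prematurely, regardless of cause, should undergo Early Discontinuation Study Visit". The schedule in Appendix A shows no assessment after that visit for a subject who withdraws. Section 4.5.1 also says: "In any case, every effort must be made to undertake safety follow-up procedures". It does not say for how long, or whether new events are to be sought.

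**What would show early departure.** SAP 9.1 plans completion frequencies, reasons for premature discontinuation, a CONSORT diagram by arm and a "Listing of all dropouts along with reason for termination and supportive information if available, treatment and time of termination". SAP section 8 derives a study duration, but it runs from the first visit, which is screening and may fall 28 days before dosing. No SAP output uses it.

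**The concern.** A crude percentage compares arms fairly when both are watched for about the same time. Here the watching can end because of the efficacy outcome. If one arm relapses more and its subjects leave the study, its later adverse events may go unrecorded, yet those subjects stay in the denominator as if they had been seen to Day 90.

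Safety is part of the primary objective and the arm-by-arm percentages are the harm comparison that readers will use. If more placebo subjects left, bertilimumab could look somewhat more harmful than it is. If more bertilimumab subjects left, some harm could be missed. The documents do not indicate which arm, if either, will lose more.

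**Working it through.** The plan states no AE, relapse or dropout rate, so there is no figure of its own to reproduce. What follows is an illustration.

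**From the documents:** safety window of 90 days (Protocol 8.3.7); infusions on Days 0, 14 and 28 (5.2); up to 42 subjects at 2:1 (8.1 and 8.2), so 42 × 2/3 = 28 and 42 × 1/3 = 14.

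**Assumed:** the same constant hazard of a first event in both arms; 90-day risk R; a share w withdrawn on day d; no events captured after withdrawal.

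**Formulas**
- Hazard: λ = −ln(1 − R)/90
- Crude incidence: (1 − w)R + w[1 − exp(−λd)]
- Mean follow-up: 90(1 − w) + dw

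**Central case** (R = 30%, d = 42, w = 30% against 10%)
- λ = 0.3567/90 = 0.00396 per day; 1 − exp(−0.00396 × 42) = 0.153
- Arm with more withdrawals: 0.70 × 0.30 + 0.30 × 0.153 = 25.6%
- Other arm: 0.90 × 0.30 + 0.10 × 0.153 = 28.5%
- Gap 2.9 points, ratio 1.11. If placebo is the arm with more withdrawals, 14 × 0.029 = 0.41 of a subject.

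**Range**

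| R | w (more / less) | d | Crude (more / less) | Gap, points | Subjects of 14 | Mean follow-up, days |
|---|---|---|---|---|---|---|
| 10% | 20% / 10% | 56 | 9.3% / 9.6% | 0.4 | 0.05 | 83.2 / 86.6 |
| 30% | 30% / 10% | 42 | 25.6% / 28.5% | 2.9 | 0.41 | 75.6 / 85.2 |
| 60% | 30% / 10% | 35 | 51.0% / 57.0% | 6.0 | 0.84 | 73.5 / 84.5 |
| 70% | 40% / 10% | 28 | 54.5% / 66.1% | 11.6 | 1.63 | 65.2 / 83.8 |

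Across R of 10 to 70%, withdrawal of 20/10, 30/10, 40/10 and 50/20%, and d of 28, 42 or 56, the gap runs from 0.4 to 11.6 points and the ratio from 1.03 to 1.31.

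**Against sampling error.** Exact 95% intervals are 8.4 to 58.1% for 4/14 and 13.2 to 48.7% for 8/28.

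**Where the gap vanishes or reverses**
- All events by Day 28 and withdrawals later: no gap.
- Events captured to Day 90 in withdrawn subjects: 30% in both arms.
- Every relapse withdrawal itself counted as an AE, with other events at R = 30%: w + (1 − w)R gives 0.30 + 0.70 × 0.30 = 51% against 0.10 + 0.90 × 0.30 = 37%. The arm that relapses more then looks less safe.

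**Does a person-time rate repair it?** Under the constant hazard of the central case, yes: both arms give 0.40 first events per 100 subject-days. With front-loaded events, no. Take 30% risk in both arms, all events by Day 28 (mean Day 14), and 10% against 30% withdrawn at Day 35:
- Subject-time, 10% withdrawn: 0.30 × 14 + 0.70 × (0.90 × 90 + 0.10 × 35) = 63.4 days
- Subject-time, 30% withdrawn: 0.30 × 14 + 0.70 × (0.70 × 90 + 0.30 × 35) = 55.7 days
- Crude incidence is correctly 30% in both arms, but the rate ratio is 55.7/63.4 = 0.88, which is spurious.

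**The case against.** The case for leaving the plan alone is substantial.

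- **Shorter observation is not prescribed.** Withdrawal on relapse is discretionary, and Protocol 4.5.1 asks for every effort at safety follow-up. Protocol 4.5.2 and 7.4 require known events to be followed to resolution or stabilisation, and 7.2 covers later related SAEs. This stands, with one limit: none of these provisions sets a period for collecting new, non-serious events after withdrawal.
- **The defining clause concerns exposure to drug, not follow-up.** This stands. The last infusion is on Day 28, so a withdrawal after that leaves dosing unchanged. The problem comes from the fixed denominator together with early exit, not from that phrase alone.
- **Unequal dropout would be visible.** This stands in large part. With up to 42 subjects, the SAP 9.1 listing and CONSORT diagram would show who left and when. A listing still gives no time at risk by arm and no estimate that allows for it.
- **The analysis is descriptive and the arms are small.** This stands. In most of the range, the distortion is under one placebo subject.

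A reader might infer that the arm that relapses more will look safer. The documents do not support that as a general statement. It requires unequal withdrawal, incomplete later follow-up and events that continue to accrue. It can also reverse, because Protocol 7.1 includes worsening of the concomitant disease in the AE definition while its later sentence on disease-related events leaves unclear whether a relapse counts. A reader might also infer that person-time rates should replace the crude ones, or should govern once follow-up differs by some margin. The front-loaded example shows why not.

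**Conclusion.** The gap in the plan is real but modest. Both documents report TEAEs only as subjects with an event over all exposed, participation can end on relapse, and nothing planned summarises time at risk by arm. For events that accrue over the 90 days, crude incidence may be understated in the arm with more withdrawals. In the central case this is 2.9 points, or 0.4 of a subject among 14; the range of 0.4 to 11.6 points comes entirely from assumed withdrawal shares, withdrawal days and event risks, with no capture after withdrawal. With equal withdrawal or complete follow-up it is zero, and events clustered around the infusions are little affected. The crude table therefore remains a sound main display; what it lacks is the follow-up information needed to read it. This is a low-cost improvement, not a flaw that undermines the safety analysis.

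**What to change.** In SAP 9.3:

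1. Keep the crude incidence tables as the main display.
2. Add, by arm, a summary of days from first infusion to last AE assessment. Do not use the study duration of SAP section 8, which starts at screening. Count any AE assessment made after the Early Discontinuation visit. The SAP safety set (6.1) also admits subjects with premedication but no infusion; they have no start date under this definition, so say how they are shown.
3. For any TEAE, SAEs and each system organ class, show beside the crude rate either a Kaplan-Meier cumulative incidence to Day 90 or an exposure-adjusted incidence (subjects with a first event over subject-time to first event or end of follow-up), labelled supportive only. Set no threshold at which conclusions move to these estimates.

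The cost is SAP wording and a few table columns built from dates already collected. No protocol amendment, visit or patient is added. The downside is that both supportive estimates assume non-informative censoring, which relapse withdrawal may breach, and the exposure-adjusted rate also assumes a roughly constant hazard. Kaplan-Meier avoids the second assumption.

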8.3.7.2 Clinical Laboratory

All laboratory data will be listed in original and standardized units; abnormal results will be flagged, depending on the direction of the change with respect to below or above the normal ranges, as high or low.

Treatment-emergent laboratory abnormalities (those that newly emerge during the observation period) will be summarized by treatment arm in terms of crude incidence rates.

Algorithms for the standardization of numeric values obtained from different laboratories and/or using different normal ranges will be defined in the SAP. In the evaluation of laboratory abnormalities, missing baseline values for subjects who had other assessments will be imputed by the mean of the normal range boundaries.

Numeric laboratory variables, transformed to standard units, as assessed at baseline, at each scheduled time point during the observation period and at the last available timepoint during the observation period will be summarized by descriptive statistics (i.e., mean, median, standard deviation, standard error, quartiles, minimum and maximum) by treatment group both for observed values and for changes from baseline. In this evaluation, subjects will be included who had the baseline and the relevant assessment.

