 - Systemic fungal infection within 90 days of the screening visit.
- 18. Current or history of positive serology of hepatitis B or C, or human immunodeficiency virus (HIV) infection.
- 19. Congenital or acquired immunodeficiency (e.g., common variable immunodeficiency, organ transplantation).
- 20. Clinically significant abnormal laboratory test results, unless regarded by the Investigator as related to UC, including but not limited to:
 - Hemoglobin level < 10.0 g/dL
 - White blood cell count $< 3 \times 10^3/\mu$ L
 - Lymphocyte count $< 0.5 \times 10^3/\mu L$
 - Platelet count $< 100 \text{ x } 10^3/\mu\text{L or} > 1200 \text{ x } 10^3/\mu\text{L}$
 - Alanine aminotransferase (ALT) or aspartate aminotransferase (AST) > 3 \times the upper limit of normal (ULN)

- Alkaline phosphatase >3 × ULN
- Serum creatinine > 2 × ULN.
- 21. Active abuse of alcohol or drugs.
- 22. Known malignancy or history of malignancy that could reduce life expectancy.
- 23. Any condition, which in the opinion of the Investigator, would place the subject at an unacceptable risk if participating in the study protocol.
- 24. Participation in a clinical trial of an investigational (unapproved) product within 1 month of the screening visit.

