5.6.7 Safety Laboratory Assessments

Clinical laboratory assessments will be performed by a central laboratory. Investigators at each site will review these laboratory data for safety considerations. Hematology and biochemistry will be conducted at all study visits. Screen for active/latent mycobacterium tuberculosis (TB) infection and *Clostridium difficile* toxin stool assay will be conducted at screening only. Anti-bertilimumab antibodies will be evaluated from Day 0 until the end of the study. Pregnancy test for women of childbearing potential will be conducted at Screening (serum) and before each study drug infusion (urine).

Safety laboratory sampling will be performed as follows by a central laboratory:

Evaluations	Parameters
Hematology	Hematocrit, hemoglobin, platelet count, red blood cell count, reticulocytes, white blood cell count with differential count
Biochemistry	Alanine aminotransferase, alkaline phosphatase, α-amylase, aspartate aminotransferase, calcium, cholesterol, creatinine, gamma-glutamyl transferase, glucose, potassium, sodium, total bilirubin, triglycerides, urea/BUN
Immunology*	Anti-bertilimumab antibodies
Pregnancy test	Serum β-hCG pregnancy test at Screening Urine β-hCG on dosing days (pre-dose)
	Urine B-hCG on dosing days (pre-dose)

The volume of blood to be drawn for each subject and processing and storage of samples are detailed in the Laboratory Manual.

All laboratory tests with values that became abnormal and are considered clinically significant after drug administration will be repeated as clinically indicated until the values return to normal, or until the etiology has been determined and the condition considered stable. Abnormal laboratory test results that are considered to be clinically important by the Investigator will be reported as an AE in the AE CRF. A laboratory abnormality will not be considered an AE unless:

- Intervention is required
- Changes in dose are required (decrease, discontinued, interrupted)
- Other treatment/therapy is required
- It is associated with other diagnoses.

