#### **Laboratory Sample Collection**

• Descriptive statistics of laboratory results, including frequency of normality for tests over time and summary of shift in results post-treatment (e.g. shift tables or listings, as relevant)

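### The by-arm laboratory abnormality count takes only newly emerging abnormalities, so worsening from an already abnormal baseline is left out while marginal crossings of the normal limit are counted

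*Protocol*

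**What the plan says.** Protocol 8.3.7.2 (Clinical Laboratory) states the flag and the counting rule. On the flag: "abnormal results will be flagged, depending on the direction of the change with respect to below or above the normal ranges". On the count: "Treatment-emergent laboratory abnormalities (those that newly emerge during the observation period) will be summarized by treatment arm in terms of crude incidence rates". It gives no grade, no multiple of the limit and no clause for worsening. A missing baseline is filled in as normal: "missing baseline values for subjects who had other assessments will be imputed by the mean of the normal range boundaries". The same section lists all laboratory data and summarises observed values and changes from baseline by treatment group, with quartiles, minimum and maximum, at each scheduled time point and at the last available one.

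Protocol 8.3.7.1 (Adverse Events) uses the treatment-emergent label more widely. It includes "pre-existing medical conditions that worsen in intensity after start of study medication and within the observation period". It defines crude incidence as "the number of subjects experiencing the event divided by the number of subjects initially exposed to study drug".

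Abnormal values can be present at entry. Inclusion criterion 4 accepts screening findings that are normal or judged not clinically significant by the investigator. Exclusion criterion 20 excludes "Clinically significant abnormal laboratory test results, unless regarded by the Investigator as related to UC", and its example cut-offs include ALT, AST and alkaline phosphatase above 3 × ULN, creatinine above 2 × ULN and hemoglobin below 10.0 g/dL.

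SAP 9.3 (Laboratory Sample Collection) does not repeat the newly-emerging count. It plans descriptive statistics with "frequency of normality for tests over time and summary of shift in results post-treatment", as tables or listings, and does not name the shift categories.

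**The concern.** The count depends on two things only: which side of the normal limit the baseline value lies on, and whether any later value lies outside the range. How far a value moves plays no part. In active ulcerative colitis some subjects may plausibly enter with low hemoglobin or high platelets. For those tests the count has the least room to show further deterioration, because those subjects cannot be counted again in the same direction.

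The two neighbouring sections also use the same label in different senses, so a reader of the report could take the laboratory table to include worsening, as the adverse-event table does. Safety is part of the primary objective (Protocol 2.1). With 28 and 14 subjects under full 2:1 enrolment, a chance imbalance in baseline abnormality could also distort the comparison between arms.

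**Working it through.** The plan states no figure for this point, so there is nothing to reproduce.

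**1. The rule applied to example subjects.** Count a subject if any post-baseline flag is high or low and differs from the baseline flag. The hemoglobin limits (12 to 17 g/dL) are assumed; the documents give none.

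| Baseline → post-dose | Counted? |
|---|---|
| ALT 2.9 → 10 × ULN | No |
| ALT 0.99 → 1.01 × ULN | Yes |
| Hemoglobin 10.0 → 7.0 g/dL | No |
| Hemoglobin 12.1 → 11.9 g/dL | Yes |
| Hemoglobin missing (set to 14.5) → 9.0 g/dL | Yes |

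A change from low to high would count as new. The omission is of worsening in the same direction.

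**2. Ceiling on the count.** Take all exposed subjects as denominator; 8.3.7.1 defines this for adverse events, and I assume that it carries over. If a share b is abnormal at baseline, the maximum crude incidence is 1 − b.
- b = 20%: ceiling 80%; not countable 0.2 × 28 = 5.6 active and 0.2 × 14 = 2.8 placebo.
- b = 50%: ceiling 50%; not countable 14 active and 7 placebo.

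**3. Imbalance at baseline.** Let 30% worsen in both arms, independently of baseline status, with 50% abnormal at baseline on active and 20% on placebo. The count shows (1 − 0.5) × 30% = 15% against (1 − 0.2) × 30% = 24%, although the arms do not differ.

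**4. Chance crossings with no drug effect.** Assume a stable subject, a 95% normal range and six post-baseline visits (Visits 3 to 8), by simulation.

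| Within-subject correlation | Counted as newly abnormal | Expected of 28 / of 14 |
|---|---|---|
| 0 | 25% | 7.0 / 3.5 |
| 0.5 | 18% | 5.0 / 2.5 |
| 0.7 | 13% | 3.6 / 1.8 |
| 0.8 | 10% | 2.7 / 1.4 |
| 0.9 | 6% | 1.8 / 0.9 |

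**5. Hemoglobin illustration.** All inputs are assumed except the two floors. Baseline is normal with mean 11.5, 12.5 or 13.5 g/dL and SD 1.4, truncated at 8 or 10 (limits from exclusion criteria 8 and 20). The lower normal limit is 12.5 and the visit noise SD is 0.5. The fall case is one post-dose value equal to baseline − 2 + noise. The no-effect case is the worst of six noisy visits, so the two columns below should not be subtracted from each other. I reran this simulation and it reproduced.

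| Rule | Counted after a 2 g/dL fall | Counted with no drug effect |
|---|---|---|
| Newly low only | 22–52% | 11–18% |
| Newly low, or one step worse at 12.5, 10 and 8 | 66–81% | 18–28% |

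Between 23% and 76% of subjects start low. Among those who end below 10 g/dL, the present rule counts 1–7%. A worsening rule built only on the protocol's own limits still misses 19–34% of the falls (100% − 81% and 100% − 66%) and adds chance counts. The categories therefore need more thought than adding the entry cut-offs.

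**The case against.** The strongest reply is that this count is not the only by-arm view of laboratory safety.

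- **Adverse events.** Protocol 7.1 treats a clinically significant departure from baseline laboratory values as an adverse event, and 5.6.7 has clinically important results reported as such. Protocol 8.3.7.1 and SAP 9.3 tabulate these by arm, with worst severity. A reader might infer that a large rise from an abnormal baseline appears in no by-arm count; the documents do not support that. What remains is that this route depends on investigator judgment, and on the conditions in 5.6.7 under which a laboratory abnormality qualifies (intervention, dose change, other therapy or an associated diagnosis).
- **Change from baseline.** It is summarised by arm at each scheduled visit, with no restriction to subjects normal at baseline. A uniform 2 g/dL fall, as in step 5, would show plainly: a mean of −2.0 with standard error 0.5/√28 ≈ 0.09 in the active arm. The illustration therefore sizes the count's insensitivity, not harm that would go unseen. That no subject ending below 8 g/dL is counted in that model follows from the fixed fall and carries no extra information. The summary does show extremes, but not how many subjects worsened.
- **Repeat testing.** A reader might infer that abnormal results vanish from the last-available summary because tests "will be repeated as clinically indicated until the values return to normal". The same sentence in 5.6.7 also allows repeats to stop once the cause is known and the condition is stable, and values at scheduled visits before recovery are already summarised.
- **SAP shifts.** A reader might infer that the laboratory shift tables are normal/abnormal only. The SAP leaves the categories open, and its ECG and physical-examination shifts use three levels. The criticism is that the categories are undefined, not that they are shown to be binary.
- **Entry.** The cut-offs in exclusion criterion 20 are examples of grounds for exclusion, not admission limits, and inclusion criterion 4 applies as well. Abnormal baselines are possible, but the documents do not say how common they are.

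**Conclusion.** The point holds for the objective laboratory count. As written, Protocol 8.3.7.2 leaves out same-direction worsening from an abnormal baseline, counts marginal crossings, and departs from the adverse-event rule in 8.3.7.1. The SAP does not close the gap, and no planned table explicitly classifies each subject's worst post-dose laboratory value.

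The size depends on the share abnormal at baseline, which is not given. At an assumed 20% to 50% on a given test, about 6 to 14 of 28 active and 3 to 7 of 14 placebo subjects could not be counted as worse in that direction. The example subjects in step 1 follow from the rule itself, given the assumed hemoglobin limits; steps 2 to 5 rest on assumed shares, correlations and distributions.

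This is a safety-reporting gap in an exploratory, descriptive trial. It does not affect the primary endpoint, alpha or sample size, and it does not mean that serious laboratory worsening would go unreported. It is still worth correcting, because safety is part of the primary objective and the data are already collected.

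**What to change.** In Protocol 8.3.7.2 and SAP 9.3:

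1. Define a treatment-emergent laboratory abnormality as a value that is newly abnormal, or at least one prespecified category worse than baseline in the same direction. State the denominator.
2. Prespecify enough categories, from a standard grading scale or from further multiples of the limit beyond the entry cut-offs, that a subject who enters above a cut-off as disease-related can still be counted as worse. With steps only at 1 and 3 × ULN, ALT going from 1.01 to 2.9, or from 3.1 to 12, would still be missed.
3. Tabulate baseline category by worst post-dose category, by arm, including unscheduled samples. Name these categories as the SAP's laboratory shift categories.
4. Report newly abnormal and worsened counts separately, so that marginal crossings can be told apart from worsening.

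The cost is a change of wording and one extra table from existing data. Counted incidence will rise noticeably in both arms, including from chance: in the assumed hemoglobin model with steps at 12.5, 10 and 8 g/dL, the no-effect count goes from about 11–18% to 18–28%. Finer categories would change these figures, and marginal crossings would still be counted, though now visible as such.
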